Subjects will receive study treatment as continuous 28-day cycles. Treatment cycles will be counted continuously regardless of dose interruptions. Subjects will undergo safety and efficacy assessments as defined in the Schedule of Procedures/Assessments ([Table 6](#)) and in the Schedule of Assessments After the Data Cutoff for the Primary Analysis ([Table 7](#)). After the data cutoff for the primary analysis subjects will be eligible to receive study treatment as continuous 56-day cycles.

Subjects will discontinue study treatment upon evidence of progressive disease, as judged by the investigator. After disease progression, subjects will be followed for survival and PFS2 until the data cut-off for the primary analysis.

This study will consist of 2 phases, the Prerandomization Phase and the Randomization Phase with treatment continuing after the data cutoff for the primary analysis. An overview of the study design is presented in [Figure 8](#).

The data cutoff for the primary analysis will occur when all randomized subjects in the Randomization Phase have completed Week 24 assessments or have discontinued study treatment prior to Week 24. After the primary analysis is completed, subjects still receiving study treatment may continue taking lenvatinib and everolimus after the data cutoff for the primary analysis. Subjects will continue to receive investigational product after the data cutoff for the primary analysis until

they complete the Off-treatment visit. The definition of the **End of Study** is the last subject's last assessment (Off-Treatment Visit) after the data cutoff for the primary analysis.

The data obtained after the data cutoff for the primary analysis will be summarized and included in the CSR at the end of study as an addendum.

[figure not shown]

Figure 8 Study Design for Study E7080-G000-218

R = randomization

PD = progressive disease

PFS2 = PFS after next line of therapy

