9.4.2.9 Management of Thromboembolic Events

Subjects should be advised to pay attention to symptoms suggestive of venous thromboembolic events, which include acute onset of shortness of breath, dyspnea, chest pain, cough, hemoptysis, tachypnea, tachycardia, cyanosis, and deep-vein thrombosis (DVT) signs including lower-extremity swelling, and warmth to touch or tenderness. In case any of these symptoms appear, subjects should be instructed to report such symptoms promptly to the treating physician. If a thromboembolic event is confirmed, instructions contained in

[Table 2](#), “Dose Modification Guidelines for Lenvatinib-Everolimus Combination Treatment-Related Toxicity,” should be followed. Appropriate supportive care should be provided together with close monitoring. If a subject experiences life-threatening (Grade 4) thromboembolic reactions, including pulmonary embolism, the study drug must be discontinued.

Arterial thromboembolic events (eg, new onset, worsening, or unstable angina, myocardial infarction, transient ischemic attack, and cerebrovascular accident) of any grade require study treatment discontinuation.

9.4.2.10 Management of Posterior Reversible Encephalopathy Syndrome/Reversible Posterior Leukoencephalopathy Syndrome

In clinical studies with lenvatinib, events of posterior reversible encephalopathy syndrome/reversible posterior leukoencephalopathy syndrome (PRES/RPLS) were reported for less than 1% of lenvatinib-treated subjects. PRES/RPLS is a neurological disorder that can present with headache, seizure, lethargy, confusion, altered mental function, blindness, and other visual or neurological disturbances. Mild to severe hypertension may be present. MRI is necessary to confirm the diagnosis of PRES/RPLS. Appropriate measures should be taken to control BP. In subjects with signs or symptoms of PRES/RPLS, instructions contained in [Table 2](#), “Dose Modification Guidelines for Lenvatinib-Everolimus Combination Treatment-Related Toxicity,” should be followed.

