9.7.1.7.1 PHARMACOKINETIC/PHARMACODYNAMIC ANALYSES

Lenvatinib and everolimus exposure parameters (AUC or concentration at the time of the event or cumulative AUC, as appropriate) derived from the population PK analysis will be related to biomarker, safety, and efficacy data using a model-based approach. For some PK/PD analyses, data from this study will be pooled with data from the Phase 2 Study E7080-G000-205 (Study 205).

For the exposure-response relationship for biomarkers (e.g., VEGF, Ang-2), data will be analyzed using a model-based approach with indirect PK/PD models.

For efficacy, a tumor growth inhibition model based on longitudinal tumor size measurements of target lesions will be included. Study drug exposure for lenvatinib and everolimus and/or measured biomarkers (e.g., VEGF, Ang-2) will be investigated as predictors and/or correlations with tumor burden changes in the tumor growth inhibition model, whenever possible using a mechanism-based approach.

Other analyses will include logistic regression analysis for ORR_{24w}, KM plots of PFS data, and Cox-regression analysis. For the Cox-regression analysis of PFS, adjustment will be made for subject's baseline characteristics or tumor-related features. In addition to lenvatinib and everolimus exposure, changes in biomarker concentrations and/or tumor burden will be related to PFS, whenever possible using a mechanism-based approach.

For the exposure-response relationship of safety, the model-based analysis will include the following AEs: hypertension (systolic and diastolic BP), triglyceridemia (and cholesterolemia), glycemia, proteinuria, weight loss, fatigue, nausea, vomiting and diarrhea. For hypertension, triglyceridemia (and cholesterolemia) and glycemia, data will be analyzed using an indirect-response model. For proteinuria, urine dipstick and/or 24-hour urine data will be analyzed using a longitudinal categorical logistic regression analysis with Markov element. For weight loss, fatigue, nausea, vomiting, and diarrhea, data will be analyzed using a longitudinal categorical logistic regression analysis. For time to treatment discontinuation due to an AE and time to first dose reduction, KM plots stratified by lenvatinib exposure will be prepared.

Population PK and PK/PD analyses will be detailed in a separate analysis plan.

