5.6.2.1 Extent of Exposure to Study Treatment

Treatment duration and the total number of treatment cycles will be summarized descriptively. The maximum number of treatment cycles for each subject is the largest cycle number in which a subject receives any non-zero dose of study drugs. The number and percentage of subjects treated within each cycle will also be summarized for each treatment arm.

Treatment duration will be summarized descriptively for each individual drug and overall. The dosing end date will be imputed to the analysis cutoff date if the subject is still on treatment at the time of the data cutoff, and the dose will be imputed with the last dose recorded in the database for that subject.

The duration of each individual drug in months will be calculated as $(\text{Date of the last non-zero dose} - \text{Date of the first non-zero dose} + 1)/30.4375$ for the specific drug, including drug interruption days. For overall treatment duration, it is defined as the duration between the earliest first dose start date of study drugs and the latest last dose end date of study drugs.

In this study, study drugs refer to lenvatinib 14 mg, lenvatinib 18 mg, and everolimus 5 mg.

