5.6.2.3 Study Drug Dose Reductions and Interruptions

DOSE REDUCTIONS

Dose reduction refers to a situation that a dose level was reduced from the previous dose level without going back. Dose reduction could apply to any of the study drugs: lenvatinib 18 mg/day (could reduce to 14, 10, 8, and 4 mg/day), lenvatinib 14 mg/day (could reduce to 10, 8, and 4 mg/day), and everolimus (5 mg every day could reduce to 5 mg every other day).

DOSE INTERRUPTIONS

Dose interruption refers to a situation that a subject had a planned temporary break from taking the study drug for a short period (ie, interruption period). Dose interruption could apply to any of the study drugs.

Dose interruption only refers to the scenario that the dose levels or dosing frequencies before and after interruption period (defined as the period with dose=0) are the same. For example: 18 mg lenvatinib followed by 0 mg and followed by 18 mg lenvatinib; 5 mg everolimus every day followed by 0 mg followed by 5 mg everolimus every day. If the dose level after dose interruption period was reduced from the dose level before the interruption period, it should be counted as dose reduction and should not be counted as dose interruption. The following 2 scenarios are examples of dose reduction instead of dose interruption:

- (1) 18 mg lenvatinib followed by 0 mg followed by 14 mg lenvatinib;
- (2) 5 mg everolimus every day followed by 0 mg followed by 5 mg everolimus every other day;

Please note, for the 2 scenarios above, the period with dose=0 should be counted as dose reduction period and not dose interruption (ie, the dose reduction date should be the date of dose=0). If the subject discontinued from treatment permanently after dose interruption with dose=0, it should be counted as treatment discontinuation instead of dose interruption.

The number of subjects with dose reductions and dose interruptions for each individual study drug will be summarized. Number (ie, frequency) of dose reductions per subject will also be summarized.

Time to first dose reduction is defined as the time period from the first dose date to the date of first dose reduction, or the time period from the first dose date to the date of first dose interruption for those subjects who had dose interruption first and then followed by dose reduction. Time to first dose reduction will be derived and summarized descriptively for each individual drug and overall for those subjects who had dose reduction during treatment period.

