Median time to first dose reduction with 95% CI will also be estimated based on Kaplan-Meier method for all the treated subjects. Subjects who did not have dose reductions during treatment period will be censored at the date of last dose.

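### The Kaplan-Meier median time to first dose reduction comes too early as an estimate for all treated subjects, because permanent stops without a reduction are censored at last dose

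*SAP*

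**What the plan says.** SAP 5.6.2.3 states the estimator and its population: "Median time to first dose reduction with 95% CI will also be estimated based on Kaplan-Meier method for all the treated subjects". The censoring rule follows: "Subjects who did not have dose reductions during treatment period will be censored at the date of last dose". It makes no distinction by reason for stopping.

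Three other SAP provisions bear on how the rule works:
- Section 5.6.2.1, for subjects continuing at cutoff: "The dosing end date will be imputed to the analysis cutoff date if the subject is still on treatment". For them, censoring at last dose is ordinary administrative censoring.
- Section 5.6.2.3, for a permanent stop that follows a zero-dose period: "If the subject discontinued from treatment permanently after dose interruption with dose=0, it should be counted as treatment discontinuation instead of dose interruption". Such a subject, if never reduced before, is censored.
- Section 5.6.2.3, for frequency: "The number of subjects with dose reductions and dose interruptions for each individual study drug will be summarized". The section also summarises the number of reductions per subject and a descriptive time to reduction among those who had one.

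The protocol has several routes to a permanent stop that need no earlier reduction. Section 9.1: "Subjects will discontinue study treatment upon evidence of progressive disease, as judged by the investigator". Table 2 ends treatment for Grade 4 toxicity, apart from laboratory abnormalities judged not life-threatening. Section 9.4.2.9 says that arterial thromboembolic events "of any grade require study treatment discontinuation".

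Neither document mentions competing risks or cumulative incidence.

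**The concern.** Kaplan-Meier treats a censored subject as still exposed to the event, at the same rate as those who remain under observation. That is reasonable for a subject still on drug at cutoff. It is not reasonable for one who has stopped for good, because no dose is left to reduce. Censoring these subjects spreads their probability over those still on treatment, so the curve falls to 50% before half of the treated subjects have had a reduction.

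Stops for toxicity add a second difficulty. A subject taken off drug outright for a severe event is handled like one who is tolerating the full dose at cutoff. Such stops are unlikely to be independent of the risk of reduction. So the alternative reading of the KM median, as the time to reduction had everyone stayed on treatment, is not assured either.

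What is at stake is a comparison of tolerability between arms. Tolerability is a secondary objective, and Protocol 7.2 cites simulations suggesting fewer dose reductions with the 14-mg start. This median is the only planned estimate of the timing of reductions that covers all treated subjects. If stops for progression or toxicity differ between arms, the two medians are displaced by different amounts.

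**Working it through.** The documents state no figure for time to first dose reduction, so there is nothing to reproduce. The check compares two quantities under stated assumptions.

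**Inputs.** From Protocol 7.1: 84.3% of the combination arm in Study 205 had a lenvatinib reduction and/or interruption. Because this counts interruptions, it is an upper proxy for the share ever reduced. From SAP section 4: 153 subjects per arm. Assumed: constant hazards, h1 for first reduction and h2 for stopping first without one. Also assumed: F, the share ever reduced before stopping, varied from 0.50 to 0.90. Only 0.843 comes from a document figure.

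**Direction.** The Aalen-Johansen estimate weights each reduction by the probability of being neither reduced nor stopped. One minus KM weights it by the KM probability of being unreduced, which is never smaller. So KM reaches 50% no later than the cumulative incidence does, whatever the hazards.

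**Size.** With F = h1/(h1+h2), the total hazard is h1/F.
- KM median: 1 − exp(−h1·t) = 0.5, so t = ln 2 / h1.
- Cumulative incidence: F·[1 − exp(−h1·t/F)] = 0.5, so t = −(F/h1)·ln(1 − 0.5/F).
- Ratio of the second time to the first: −F·ln(1 − 0.5/F) / ln 2.
- Share actually reduced at the KM median: F·(1 − 2^(−1/F)).

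At F = 0.843: 0.5/0.843 = 0.593; ln(0.407) = −0.899; 0.843 × 0.899 = 0.758; 0.758/0.693 = 1.09.

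| F (ever reduced) | Time to 50% incidence ÷ KM median | Share actually reduced at KM median |
|---|---|---|
| 0.90 | 1.05 | 48% |
| 0.843 | 1.09 | 47% |
| 0.765 | 1.17 | 46% |
| 0.70 | 1.27 | 44% |
| 0.60 | 1.55 | 41% |
| 0.50 | never reached | 38% |

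**Absolute scale.** Suppose 60% are reduced and 15% have stopped unreduced by day 168. The total hazard is ln 4/168 = 0.00825 per day, and h1 = (0.60/0.75) × 0.00825 = 0.00660. The KM median is ln 2/0.00660 = 105 days (3.45 months). The cumulative incidence reaches 50% where 0.8·[1 − exp(−0.00825·t)] = 0.5, at 119 days (3.91 months). The gap is 0.46 months.

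**Difference between arms.** Let both arms have a KM median of 8 weeks, with F = 0.843 in one and 0.70 in the other. Half of the subjects are reduced by 8 × 1.094 = 8.8 weeks in the first arm and 8 × 1.265 = 10.1 weeks in the second. KM shows no difference.

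**Simulation.** There were 1,000 runs per scenario with 153 subjects, an assumed KM median of 8 weeks, and uniform administrative censoring over weeks 24 to 150. Medians in weeks, KM against cumulative incidence, were 7.9 and 8.7 (F = 0.843), 8.0 and 9.3 (0.765), 7.9 and 10.1 (0.70), and 8.0 and 12.5 (0.60). The crude proportion reduced was 0.838, 0.762, 0.699 and 0.600, close to the final cumulative incidence of 0.843, 0.765, 0.701 and 0.601. The planned crude count is therefore sound.

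**The case against.** The strongest reply is that this is a descriptive exposure summary, with no test, hazard ratio or decision rule attached. The primary safety endpoint is a proportion with adverse events within 24 weeks and does not use it. The SAP also reports reasons for stopping treatment (5.2.2) and the proportion and timing of stops for toxicity (5.6.3.6), so a reader could see whether the arms differ in early stops. KM censored at last dose can also be read as time to reduction while on treatment. All of this limits the weight of the point. It does not repair the median: the crude count carries no timing, the descriptive time covers only subjects who were reduced, and the on-treatment reading is not what all treated subjects implies.

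Three stronger readings are tempting, and the documents do not support them.
- A reader might infer that the plan overstates how often doses are reduced. Section 5.6.2.3 asks only for a KM median and its interval. It plans no KM curve or percentage, and takes frequency from crude counts.
- A reader might take the 23.5% of Study 205 combination subjects who stopped for adverse events (Protocol 7.1) as the share who stop unreduced. That figure counts stops regardless of earlier reductions. Under Table 2 of this protocol, lenvatinib is reduced at the first three occurrences of intolerable Grade 2 or Grade 3 toxicity and treatment stops at the fourth, so a subject who stops by that route has already had the event.
- A reader might extend the point to Protocol 9.7.1.7.1, where for "time to first dose reduction, KM plots stratified by lenvatinib exposure will be prepared". That section gives no censoring rule and defers details to a separate analysis plan, so whether those plots are affected cannot be judged.

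**Conclusion.** The point holds for the KM median in SAP 5.6.2.3. As an estimate for all treated subjects it is too early. The direction follows from the estimators; the size depends on constant hazards and on an assumed share ever reduced. Measured against the KM median, the time at which half have been reduced is 5 to 17% later for shares of 90% to 76.5%, and about 9% later at the Study 205 proxy. Since that proxy includes interruptions, the reduction-only share may be lower and the shift larger. It is 55% at a share of 60%. At 50% or below, the SAP could report a median that the treated population never reaches. The documents give neither a reduction-only rate for lenvatinib nor a rate of stopping unreduced, so these remain illustrations. Neither the non-inferiority test nor the sample size is touched. This is a worthwhile, low-cost improvement to a secondary description of tolerability.

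**What to change.** In SAP 5.6.2.3, report by arm the Aalen-Johansen cumulative incidence of first dose reduction with 95% CI, for example at Weeks 4, 8 and 24, together with the time at which it reaches 50% if it does. Define permanent discontinuation or death without a prior reduction as the competing event, and censor only subjects still on treatment at data cutoff. If the KM median is kept, label it as conditional on remaining on treatment.

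The cost is a wording change and a different estimator applied to data already collected. The one drawback is that a 50% time may not be reached, in which case the table should say so.

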5.6.3 Adverse Events

Adverse events will be graded according to the National Cancer Institute Common Terminology Criteria for Adverse Events (NCI-CTCAE), Version 4.03. The AE verbatim descriptions (investigator terms from the CRF) will be classified into standardized medical terminology using the MedDRA Version 22.1 or higher. Adverse events will be coded to the MedDRA lower level term (LLT) closest to the verbatim term, the linked MedDRA preferred term and primary system organ class are also captured in the database.

A treatment-emergent AE is defined as any one of the followings:

- An AE that emerges during treatment or up to 28 days after the last dose of study treatment, having been absent at pretreatment (baseline); or
- An AE that reemerges during treatment or up to 28 days after the last dose of study treatment, having been present at pretreatment (baseline) but stopped before treatment; or
- An AE that worsens in toxicity grade during treatment or up to 28 days after the last dose of study treatment, relative to the pretreatment state, when the AE is continuous; or
- An AE with missing or partial onset date and is considered related to study treatment by investigator; or
- An AE that is not treatment-related and with missing or partial onset date will be considered as treatment-emergent unless the onset of the AE can be determined as earlier than the first dose date or later than 28 days after the last dose of study treatment.

Unless otherwise specified, a subject will be counted only once at each level of summary (eg, SOC and/or PT), even if the subject experienced more than 1 TEAE within a specific SOC and/or PT.

5.6.3.1 Overview of TEAEs

An overview of TEAEs reported through the study will be provided for each treatment arm. Overall summary of TEAE will include the number and percentage of subjects with TEAEs, serious TEAEs, treatment-related TEAEs, intolerable Grade 2 TEAEs, TEAEs of Grade 3 or higher, TEAEs leading to treatment discontinuation (discontinuation of both study drugs in each treatment arm), TEAEs leading to dose reductions, TEAEs leading to dose interruptions, and TEAEs with fatal outcomes. Overview of TEAEs episodes adjusted by treatment duration will also be provided.

An overview of TEAEs reported for those 32 subjects who had received ≥ 2 incorrect lenvatinib doses due to IxRS issue will also be provided.

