- p. Screening CT of the brain with contrast or MRI of the brain pre- and post-gadolinium should be performed within 28 days of randomization. Subjects with protocol-eligible treated brain metastases must also have brain CT/MRI performed at all tumor assessment time points (eg, every 8 weeks). For other subjects, brain scans should be performed as clinically indicated and to confirm CR. The same methodology (CT or MRI) and scan acquisition techniques that were used for the screening assessments should be followed during the Randomization phase. A brain scan will be performed within a target of 1 week but no more than 2 weeks following achievement of a CR.
- q. HRQoL will be assessed at Baseline, on Day 1 of each subsequent cycle starting with Cycle 2, and at the Off-Treatment Visit. Every effort should be made to administer HRQoL surveys prior to study drug administration and before other assessments and procedures.
- r. Telephone contact or clinic visit on Day 8 (±2 days) of Cycle 1 to assess subjects for development of early toxicity. An unscheduled visit may be requested by the investigator if deemed necessary.
- s. Concomitant medications will be recorded from the Screening Visit through 28 days after the last dose of study drug. All anticancer therapy will be recorded until time of death or the data cutoff for the primary analysis unless not allowed to be provided due to confidentiality.
- t. AEs and SAEs will be recorded from the signature of Informed Consent until 28 days after the last dose of study drug. SAEs, irrespective of relationship to study drug, must be reported as soon as possible but not later than 24 hours from the date when the investigator becomes aware of the event. Signs/symptoms related to disease progression should not be reported as AEs. During treatment interruption due to AEs, repeat AE assessments should be performed at least every 7 days (until restarting study drug administration).
- u. PFS2 is defined as the time from randomization to the date of disease progression after next line of therapy or death from any cause, whichever occurs first. Subjects who discontinue treatment before the data cutoff for the primary analysis will be followed for survival every 12 weeks (±1 week) after the Off-Treatment Visit. If a clinic visit is not feasible, follow-up information may be obtained via telephone or email.

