5.6.3.5 Serious TEAEs

The incidence of serious TEAEs will be summarized as below:

- Serious TEAEs by SOC and PT
- Treatment-related serious TEAEs by SOC and PT
- Serious TEAEs by decreasing frequency of PT
- Most commonly reported (eg, $\geq 5\%$) serious TEAEs by SOC and PT
- Serious TEAEs adjusted by treatment duration

In addition, a listing of serious AEs will be provided.

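### Duration-adjusted TEAE and serious TEAE rates count events up to 28 days after the last dose but divide by time that ends at the last dose, so they are modestly overstated

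*SAP*

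**What the plan says.** **Outputs.** SAP 5.6.3.1 states "Overview of TEAEs episodes adjusted by treatment duration will also be provided". SAP 5.6.3.5 lists "Serious TEAEs adjusted by treatment duration". Neither section writes out a formula, names another measure of person-time, or limits the events to those starting on drug.

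**Numerator.** SAP 5.6.3 defines a treatment-emergent event to include "An AE that emerges during treatment or up to 28 days after the last dose of study treatment", with the same extension for events that recur or worsen. The data will contain these events. The footnotes to Table 6 in Protocol 9.5.2 say "AEs and SAEs will be recorded from the signature of Informed Consent until 28 days after the last dose of study drug". The TEAE definition in Protocol 9.7.1.8.2 does not spell out the 28-day tail; the SAP does.

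**Denominator.** SAP 5.6.2.1 defines overall treatment duration as "the duration between the earliest first dose start date of study drugs and the latest last dose end date of study drugs". The duration of each individual drug also runs from first to last non-zero dose, "for the specific drug, including drug interruption days". For those who have not stopped: "The dosing end date will be imputed to the analysis cutoff date if the subject is still on treatment". No post-dose extension appears in any of these definitions.

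**The concern.** A rate per unit of time needs events and time from the same window. Here the event window is up to 28 days longer than the time window for anyone who has stopped treatment, and the same length for anyone still on treatment at the cutoff. The rate is therefore too high, and the excess grows as treatment gets shorter and as more subjects stop.

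The adjustment is there to make the 14-mg and 18-mg arms comparable when time on treatment differs. With this denominator, some dependence on treatment duration stays in the rate. If one arm stops sooner, its rate is inflated more, and two arms with identical true rates would show a ratio other than 1. The documents do not say which arm that would be. The decision on the 14-mg dose rests on clinical judgment over all the safety and efficacy data (SAP 6; Protocol 9.7.1.6.1), so these tables may well be read even though they carry no test.

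**Working it through.** The plan states no adjusted rate, so there is no figure of its own to reproduce. The check derives the error from the SAP's definitions.

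**Inputs from the documents**
- Event window: first dose to last dose + 28 days (SAP 5.6.3).
- Time window: first dose to last dose, or to the cutoff if still on treatment (SAP 5.6.2.1).
- Interruption days are already in the duration, so they add no further mismatch.
- One month = 30.4375 days (SAP 5.6.2.1).

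**Inputs assumed, because the documents do not give them**
- T, mean treatment duration in days: 3 to 12 months.
- d, mean fraction of the 28-day window observed, averaged over all subjects: 0.6 to 1. Subjects still on treatment count as 0, and death or the cutoff shortens the window for others.

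**Formula.** Let E be the number of countable episodes and N the number of subjects.
- Rate as planned: E / (N × T)
- Rate with matched time: E / (N × (T + 28d))
- Planned / matched = (T + 28d) / T = 1 + 28d/T

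E cancels, so the factor does not depend on how often events occur or on whether the post-dose rate differs from the on-drug rate.

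**Overstatement per arm**

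| Mean duration | d = 1 | d = 0.8 | d = 0.6 |
|---|---|---|---|
| 3 months (91.3 days) | 1.307 | 1.245 | 1.184 |
| 6 months (182.6 days) | 1.153 | 1.123 | 1.092 |
| 8 months (243.5 days) | 1.115 | 1.092 | 1.069 |
| 10 months (304.4 days) | 1.092 | 1.074 | 1.055 |
| 12 months (365.25 days) | 1.077 | 1.061 | 1.046 |

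For example, at 6 months and d = 1: 1 + 28/182.625 = 1.153.

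**Spurious ratio between arms when true rates are equal.** This is the factor of the shorter-duration arm divided by that of the longer:
- 6 vs 8 months, d = 1 in both: 1.153/1.115 = 1.03
- 8 vs 10 months, d = 1 in both: 1.115/1.092 = 1.02
- 6 vs 8 months, d = 0.8 (shorter) and 0.6 (longer): 1.123/1.069 = 1.05
- 8 vs 10 months, d = 0.8 and 0.6: 1.092/1.055 = 1.03
- For contrast, 6 vs 10 months at d = 1 gives 1.06, and 4 vs 10 months gives 1.13.

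**Simulation check.** Each setting had 20,000 subjects, exponential time on treatment, cutoff 5.5 to 24 months after start, and a true rate of 2.0 episodes per month on drug and in the post-dose window. Observed mean durations were 3.8, 5.3, 6.4 and 8.1 months. The planned rate came out at 2.45, 2.30, 2.22 and 2.15. The matched denominator returned 2.00 each time.

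**The case against.** **The formula may be elsewhere.** Programming rules and table shells are in separate documents (SAP 9 and 11) that could define the denominator differently. That is possible. But the SAP uses a term it defines itself, and a programmer following its text would build the mismatch. It also leaves open whether the overall or the individual-drug duration applies; both end at a last dose.

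**Serious TEAEs may not be counted as episodes.** SAP 5.6.3.1 says episodes and 5.6.3.5 does not, while SAP 5.6.3 by default counts a subject once. This stands as a limit. The windows still differ, but the factor carries over exactly only if full treatment duration is the divisor.

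**The quantity is still interpretable.** Attributing all TEAEs to time on drug is a describable summary, and the tables are labelled as adjusted by treatment duration. That is fair, but the number is then not the event rate over the period in which events were counted.

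**Little depends on it.** The tables carry no test or boundary. The primary safety endpoint (SAP 5.6.1) is a proportion within 24 weeks of randomization and uses no person-time. Both arms take the same two drugs, and 14-mg subjects who tolerate Cycle 1 move to 18 mg, so nothing in the documents points to a large difference in duration. This objection stands and sets the severity.

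**Stronger readings a reader might infer.** One is that serious TEAEs suffer most because they cluster around stopping, perhaps doubling the error. The documents give no post-dose event rate, and against a matched denominator the event rate cancels. It matters only against an on-drug-only rate, where the excess is r × 28d/T, with r the ratio of post-dose to on-drug event rates. That could be smaller as well as larger: 7.7% at 6 months with r = 0.5 and d = 1. Another is that these are the only AE summaries allowing for unequal time on treatment. SAP 5.6.3.11 also plans summaries by treatment cycle and time to first onset of hypertension, with similar analysis for proteinuria.

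**Conclusion.** The point holds at low severity. Under the SAP's own definitions the numerator and denominator of the two adjusted tables cover different time, and episode rates are overstated by 1 + 28d/T whenever anyone has stopped treatment. For mean durations of 6 to 12 months that is about 5-15% per arm. Between arms it is about 2-5% for modest duration differences.

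These sizes rest on assumed T and d, and on reading treatment duration as SAP 5.6.2.1 defines it. It would be tempting to conclude that the safety comparison between arms is materially biased, or biased in a known direction. The documents support neither: they do not say which arm stops sooner, and a large ratio needs a large duration difference for which they give no evidence.

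**What to change.** In SAP 5.6.3.1 and 5.6.3.5, write out the rate and choose one of two matched forms:

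1. Keep the TEAE definition and divide by each subject's time from first dose to the earliest of last dose + 28 days, death or data cutoff, summed over subjects.
2. Keep treatment duration as the divisor and count only events with onset on or before the last dose.

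The same sentence should say whether 5.6.3.5 counts episodes or subjects.

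The cost is one sentence in the SAP and one derived variable (option 1) or an onset-date filter (option 2). No data collection, endpoint or test changes. Under option 1 the reported rates will be somewhat lower.
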